of life, presumably due to protection afforded by maternal antibodies. Following 2 months, the agespecific incidence of clinical episodes of malaria increases to levels near that of the second year of life (see Section D, Study Site). Thus cohort 1 should be essentially free of parasitemia during the first 5 months of age, cohort 2 will be exposed to Pf parasites until 5 months of age, and then not exposed until approximately 10 months and cohort 3 will have continuous exposure. Since SP and AS does not affect pre-erythrocytic stage exposure, all children will have pre-erythrocytic stage exposure continuously. Therefore, it is the degree of exposure to erythrocytic stage antigens that is the independent variable manipulated by the intervention. We have chosen to administer the chemoprohylaxis at 2,5 – 10,5 months and not at 2-10 months of age to avoid possible interactions between the SP+AS treatment and the responses to the EPI vaccines. The SP+AS treatment will be administered 15 days prior to the EPI vaccines (which are administered at 0, 2, 3, 4 and 9 months of age), a sufficient time lag to avoid such interactions. (Amended 15 October, 2004) (Amended 2 December, 2004) (Amended 10 August, 2005)

For our primary outcome variable, we will compare the risk of having at least one malaria episode **as detected by passive case detection** between 12-24 months in the three cohorts. We have chosen our primary outcome variable and follow-up period (12-24 months) in order to duplicate the parameters from the two previous clinical trials upon which this study is based [1, 2]. We anticipate that Cohort 2, with exposure to blood stage antigens blocked during the latter half of infancy, will have a statistically significantly higher risk of at least one episode of malaria between 12-24 months of age than will Cohorts 1 and 3, and that by the same measure, Cohorts 1 and 3 will be similar to each other in terms of risk. Because we are aware that an affect on clinical outcome could be seen even after year two, we will also include follow-up during year three consisting of home visits every 3 months. Children will continue to have full access to both the llha Josina **Maragra** Health Center and Manhiça Hospital for care. In addition, children will be followed long-term for mortality through the demographic surveillance system (DSS) already in place. **(Amended 15 October, 2004) (Amended 2 December, 2004)**

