The three cohorts are proposed in order to address the **central hypothesis**: Exposure to Pf erythrocytic stage antigens in early infancy does not contribute to the development of naturally acquired immunity to malaria but exposure after 5 months of age does contribute to the development of naturally acquired immunity. Specifically, the three cohorts are needed to address the following:

1- The comparison of Cohort 1 (prophylaxis 2-5 2,5-5,5 months) and Cohort 2 (prophylaxis 5-10

5,5-10,5 months) is the key comparison. During the first 10 months of life, we assume that both Cohorts 1 and 2 will have experienced exposure to Pf blood stage parasites, and therefore Pf erythrocytic stage antigens, since each have been left unprotected by prophylaxis during several months. We recognize that infants in the first 5 months of life are likely to have a greater degree of protection due to maternal antibodies than those who are 5-10 months of age, although there is some controversy with regard to this [72]. Nevertheless, previous data from our study site indicate that there is essentially no malaria in the first two months of life but that after 2 months, the age-specific incidence of clinical episodes of malaria increases to levels near that of the second year of life. We also recognize that younger infants may be kept more covered by their mothers and thus experience less exposure to mosquitoes. Thus, the rate of malaria acquisition in the two cohorts may not be the same. Because this will be an uncontrolled variable that may affect the outcome measures of the

Final protocol: 2nd July 2004 Amendment 1: 15th October 2004 Amendment 2: 2nd December 2004 Amendment 3: 11th July 2005 Amendment 4: 10th August 2005 Amendment 5: 12th September 2006 CONFIDENTIAL

Page 17 of 51

[figure not shown]
study, the effects of the number of episodes of parasitemia will be included in the statistical model used for analysis (see below). (Amended 2 December, 2004)

[figure not shown]

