Active case detection: Active case detection will consist of a weekly visit by the field worker to the home of the infant *from enrollment until 10,5 months of age*. During this visit an axillary temperature will be taken by electronic digital thermometer and the caretaker(s) will be questioned about any history of fever. In the case of a documented fever (axillary temperature $\geq 37.5^{\circ}$ C) or history of fever in the previous 24 hours, thick and thin blood smears will be collected, stained, and read according to quality-controlled procedures [9]. If there is no fever or history of fever, no sample will be taken. The purpose of this active case detection follow-up is to detect the first encounter with the parasite that produces clinical malaria during the first 10 months of life, the period of the intervention. The respiratory rate of the child will also be recorded, and if increased (>=60 breaths/min in children younger than 2 months and >=50 in children aged 2-12 months), the child will be taken to the health post the mother/guardian will be advised to take the child to the health post if it persists. During these weekly visits, the field worker will also inquire as to whether the child has been hospitalized for any reason or if any skin rashes (potentially indicative of adverse reaction to SP) or other signs/symptoms have developed. (Amended 2 December, 2004) (Amended 11 July, 2005)

Passive case detection: Caretakers will be asked to bring infants into the IIha Josina Maragra health post or the Manhiça health center, where a morbidity surveillance system is functioning, whenever the child is ill. We propose to only enroll families who live within close access to the IIha Josina Maragra or Manhiça health post so that they will all have access to the health facility if they wish to seek care for their children. (Amended 15 October, 2004) (Amended 10 August, 2005)

Monthy surveillance home visits: Home visits will be performed monthly from month 10.5 to month 24 of age. Parents/guardians will be asked about the health status of the child and whether he/she has been admitted to hospital since the previous visit. These visits will ensure that safety information on serious adverse events and deaths is captured. (Amended 11 July, 2005)

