The primary aim of the study is to determine the effect of timing of exposure to Pf erythrocytic stage antigens during infancy (0 to 5 vs 5 to 10 months of age) on subsequent morbidity due to clinical malaria. The primary outcome variable was chosen as the presence or absence of at least one episode of clinical malaria during the second year of life **as detected by passive case detection**, because current epidemiological data suggests that this outcome is a sensitive, inverse indicator of NAI; when used as the primary outcome variable in studies detailed earlier in this proposal (see background and rationale sections) significant differences were detected between cohorts receiving differing prophylaxis [1, 2]. In the study site, an incidence of **0.4 0.48**-episodes of clinical malaria per person year at risk ([name], personal communication). Thus, as described in the sample size section, each of the three cohorts will be compared to the others in pairwise fashion, with the p value for significance reduced to 0.017 to adjust for the three comparisons. **(Amended 15 October, 2004) (Amended 2 December, 2004)**

However, other variables could also affect the likelihood of experiencing at least one clinical episode during the second year of life, such as number of clinical episodes experienced during the first year of life, regardless of the age at which they occurred. In addition, we believe that immunological responses during the first year of life may potentially explain the differences in susceptibility to clinical episodes during the second year (secondary aim), although other factors, such as host genotype (e.g., presence or absence of sickle cell trait, α -thalassemia or others), the presence of haemoglobin AF, parasite genotype, and possibly maternal immune responses, could also affect the primary outcome variable. Because we do not know which of these many factors will be most closely associated with the outcome, we propose a logistic regression analysis to make this assessment. All of these factors will be used in a multiple logistic regression model, and those with significant associations will be identified. Although it is by no means assured, we hope that one of the immunological measurements (see below) will show a significant association and thus will serve as a positive or negative correlate with NAI. A rationale has been provided regarding the concentration of antibody responses to PfEMP-1 as a likely candidate.

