Final protocol: 2nd July 2004 Amendment 1: 15th October 2004 Amendment 2: 2nd December 2004 Amendment 3: 11th July 2005 Amendment 4: 10th August 2005 Amendment 5: 12th September 2006 CONFIDENTIAL

Page 32 of 51

A similar logistic analysis will be conducted with a second important clinical outcome: whether or not each participant experiences a Hct < 25% during the second year of life, as measured during the $\frac{12}{15}$, $\frac{15}{20}$ and $\frac{25}{24}$ month cross-sectional surveys. Although it is perhaps less clear how the immunological responses we are measuring might impact on Hct, it is nevertheless a primary indicator of morbidity and also a primary target for interventions such as anti-morbidity malaria vaccines or prophylaxis regimens, and is proposed here as a secondary outcome. (Amended 2 December, 2004)

b) Overall Interpretation of Results

Our prediction: We hypothesize that the relative risk of having at least one clinical episode of malaria in the second year of life will be 2.0 or greater in Cohort 2 as compared to Cohort 1 and 3. If this is true, it will support our hypothesis that the infant immune system is able to mount protective responses provided that exposure occurs following month 5, but cannot do so if exposure occurs earlier but is absent between months 5 to 10. This finding would have important implications for future vaccine trials, for which the timing of administration of malaria vaccines would then be judged to be critical if they are to induce protection against blood stage infection.

Another expected finding of this study is that Cohort 1, and to a lesser extent Cohort 2, will have reduced frequencies of parasitemia and clinical episodes of malaria during the first year of life, due to the protective effects of SP + AS administration. A key strategy for public health planners is how to achieve this protective effect without causing a rebound parasitemia during the second year of life. Ultimately, it may be important to repeat studies such as this in several geographic locations, in order to assess how a variety of transmission intensities, parasite genotype frequencies, host populations, vector populations, etc., may influence the relationship between the administration of prophylaxis, in particular its intensity and timing, and lasting gains in child health.

c) Additional Analyses of Clinical and Parasitological Data: Cross sectional and Prospective.

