Our prediction: We hypothesize that the level of antibodies will be statistically significantly lower in Cohort 2 as compared to either Cohort 1 or Cohort 3 at the 10 month old cross-samplings and that this reduction will correlate with an increased relative risk of one or more clinical episodes of malaria in the second year of life.

Proposed analysis: Immunological endpoints will be based upon levels of antibodies (intensity) and the ratio of Th1/Th2 cytokines at each of the cross-sectional time points. For the first analysis, values for antibodies and cytokine ratios for each cohort will be compared at each cross-sectional timepoint. For the second analysis, values for antibodies and cytokine ratios at each of the timepoints will be correlated with risk of clinical outcome(s) for each cohort and between cohorts. Immunological data will be analyzed in two different ways:

- **Cross-sectionally** the key analysis will be comparison of immunological markers between cohorts, not individuals, to show differences in the development of acquired immunity to malaria attributable to age of first exposure to Pf antigens. The key timepoint for comparison is considered to be 10 months. We will explore the profile of immune responses and how markers change with age. Specifically, we predict the following outcomes:

X1; t= 2,5 month 0 or enrollment. No difference between the 3 cohorts

X2, t=5 5,5 month: No difference between the 3 cohorts

X3, t=10 10,5 month (*key comparison*): Cohort 2 will have significantly lower levels of anti-PfEMP-1 antibodies and/or Th1/Th2 cytokine ratios than cohort 1 and 3. Cohort 1 = cohort 3. **X4**, t=12 month: same as X3.

X5- **X4**, t=15 month: same as X3.

X6, t= 20 month: No difference between the 3 cohorts.

X7- **X5**, t= 25 **24** month: same as X6. We expect the immune responses to equalize between cohorts by 20-25 months.

(Amended 2 December, 2004) (Amended 11 July, 2005)

- **Prospectively**: To look for correlates of immune responses and clinical outcome. Specifically, acquisition of immune response at the level of the individual subject (as opposed to cohort) in cohort 1 vs. 2, and correlation with how that individual responds to infection and the relative risk of clinical disease. We will evaluate whether lack of exposure at different ages (0-5 months, or 5-10 months) during first 2 years of life results in differences of antibody and/or cytokine markers between the different cohorts.

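### The number of parasitaemia episodes, which the prophylaxis itself changes, is to enter the model for the key Cohort 1 versus Cohort 2 comparison, and nothing says whether that model or the covariate-free pairwise comparison decides the primary aim

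*Protocol*

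**What the plan says.** **The key comparison.** Section D.iii, under the rationale for the three cohorts, sets prophylaxis at 2.5–5.5 months (Cohort 1) against the later window (Cohort 2): "5,5-10,5 months) is the key comparison". The same paragraph notes that malaria acquisition may differ between the two cohorts, because of maternal antibody and because young infants are kept covered. It treats this as an uncontrolled variable, for which reason "the effects of the number of episodes of parasitemia will be included in the statistical model used for analysis", with a pointer to the analysis below.

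**The analysis section.** D.xi.1.a first says that the three cohorts are compared in pairs, with the significance level lowered to 0.017. No covariates are named. It then turns to other influences on the outcome, beginning with the "number of clinical episodes experienced during the first year of life, regardless of the age at which they occurred". First-year immune responses, host genotype, haemoglobin AF, parasite genotype and maternal responses follow. Of these it says "All of these factors will be used in a multiple logistic regression model, and those with significant associations will be identified". The stated hope is to find an immunological correlate of protection.

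**What the intervention changes.** Section C says "it is the degree of exposure to erythrocytic stage antigens that is the independent variable manipulated by the intervention". D.xi.1.b expects prophylaxis to lower malaria in both treated cohorts, more in the first than in the second: they "will have reduced frequencies of parasitemia and clinical episodes of malaria during the first year of life, due to the protective effects". D.viii lists the number of first-year clinical episodes as a secondary outcome. For the 10.5-month survey, D.xi.2.a predicts that "Cohort 2 will have significantly lower levels of anti-PfEMP-1 antibodies and/or Th1/Th2 cytokine ratios than cohort 1 and 3".

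**How parasitaemia is recorded.** At the weekly visits in D.iv: "If there is no fever or history of fever, no sample will be taken". Under D.vi, the 5.5, 10.5 and 15 month surveys also determine parasitaemia only if the child has fever.

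**The concern.** The episode count is not a baseline confounder that randomisation happened to leave unbalanced. It lies on the path from assignment to second-year risk, and the protocol says so in its own words. Conditioning on it has two consequences.

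- If fewer early episodes mean less immunity, the count carries the effect under study, and holding it fixed takes that effect out.
- If children differ in underlying exposure or susceptibility, the count also reflects those differences. An unprotected child with no episodes tends to be at low risk, whereas a protected child with no episodes need not be. Comparing the two at the same count gives a difference even when assignment does nothing.

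Because smears depend on fever, the count is close to a count of clinical episodes. It is therefore a poor measure of the exposure that D.iii wants to equalise.

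At stake is the reading of the primary aim. The adjusted and the pairwise results can fall on different sides of 0.017, and the document does not say which one counts.

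**Working it through.** **1. The plan's own sample size.** For two Poisson rates of 0.4 and 0.8 per person-year, one year each, two-sided alpha 0.017 and 80% power (D.ix):

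n = (2.387 + 0.842)² × (0.4 + 0.8) / 0.4² = 10.42 × 1.2 / 0.16 ≈ 78.2, against the stated 78.

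Allowing for 20% loss, 78 / 0.8 = 97.5, so 98 as stated. The level also checks: 1 − 0.95^(1/3) = 0.01695. The stated size therefore belongs to a comparison of cohorts with no covariates.

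**2. Episode imbalance created by the design.** Inputs are the Manhiça incidence table in D.i: 35/9491 person-weeks at 2 to <6 months, 46/6134 at 6 to <8 months, 117/12963 at 8 months to <1 year. One month is 52.18/12 = 4.348 weeks.

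- 2.5–5.5 months: 3 × 4.348 × 35/9491 = 0.048 episodes.
- 5.5–10.5 months: 4.348 × (0.5 × 35/9491 + 2 × 46/6134 + 2.5 × 117/12963) = 0.171 episodes.

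Assume 90% prophylactic efficacy (not a protocol figure):

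- Cohort 1: 0.1 × 0.048 + 0.171 ≈ 0.18.
- Cohort 2: 0.048 + 0.1 × 0.171 ≈ 0.065.

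The ratio is about 2.7.

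**3. Effect of adjusting.** A logistic model for any second-year episode was fitted to simulated data (200,000 infants per arm), with and without the first-year count. The second-year rate was 0.4 per person-year. Children's rates varied log-normally around these values, so mean counts rise with the SD while the 2.7 ratio holds. Entries are odds ratios, Cohort 2 versus Cohort 1. Tripled incidence is a sensitivity bound, not a protocol figure.

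| Scenario | Incidence as in step 2: unadjusted → adjusted | Three times that: unadjusted → adjusted |
|---|---|---|
| No effect, no heterogeneity | 1.00 → 1.00 | 1.00 → 1.00 |
| No effect, log-rate SD 0.7 | 1.00 → 1.08 | 1.00 → 1.21 |
| No effect, log-rate SD 1.0 | 1.00 → 1.17 | 1.00 → 1.40 |
| Effect wholly through episodes, each halving the later rate | 1.07 → 0.99 | 1.24 → 1.00 |
| Effect wholly through episodes, each quartering the later rate | 1.12 → 1.00 | 1.38 → 1.00 |

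The last two rows have no heterogeneity between children.

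**4. Direction and another form of heterogeneity.** With gamma heterogeneity of variance 1 and no true effect, means of 0.18 and 0.065 give an adjusted odds ratio of about 1.1. Assumed means of 0.5 and 0.15 give 1.30. Reversing the two pairs of means gives about 0.90 and 0.77.

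**5. False-positive rate at nominal 0.017.** Amendment 5 sets 350 in total: 350/3 ≈ 117 per arm, less 20% ≈ 93. With log-normal SD 1.0 and 1,500 trials, rejection is 0.013 unadjusted against 0.028 adjusted. At three times the incidence it is 0.019 against 0.084. With the gamma model at 0.18 and 0.065 it stays at about 2%.

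**The case against.** **A comparison as randomised is arguably already planned.** D.ix and D.xi.1.a describe pairwise comparisons at 0.017 with no covariates, and the sample size reproduces on that basis. The natural reading of D.xi.1.a is a primary comparison followed by an explanatory model. This largely stands: a reader might infer that no randomised comparison exists, and the text does not support that. What remains is that D.iii attaches the episode count to the key comparison, and no sentence ranks the two analyses.

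**Immune responses and parasite genotype.** A reader might infer that these too are in the key model. They are named only in the D.xi.1.a regression, whose stated purpose is to find correlates. Nothing says that cohort is a term in it. The only link is the pointer in D.iii.

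**The investigators may have wanted the effect of age at equal exposure.** Section A says age and duration of exposure have been hard to separate, so that is a legitimate question. Entering a count of mostly febrile episodes does not answer it without bias, since the count itself reflects susceptibility.

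**The direction of bias.** It is tempting to say that the adjustment favours the prediction that Cohort 2 does worse. That follows if Cohort 1 has more first-year episodes, as the D.i table implies. D.xi.1.b expects the larger reduction in Cohort 1, which would turn the bias round. Mediation pulls the estimate towards no effect. D.ix also records incidence below expectation, which argues against the high-incidence results.

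**Conclusion.** The point holds for the number of parasitaemia episodes. D.iii commits the key comparison to a covariate that the intervention alters, D.xi.1.a describes a comparison without it, and the document leaves open which one answers the primary aim. A cohort contrast adjusted in that way is no longer protected by randomisation.

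The size is modest on the protocol's own rates: a null odds ratio of about 1.1, given 90% efficacy and substantial variation between children. The 1.3 to 1.4 results need higher first-year incidence than the D.i table gives. A mediated effect of 1.07 to 1.38 would be adjusted away to about 1.00. These are illustrations, and the documents establish neither the size nor the direction. The finding rests on the status of the covariate and the missing hierarchy, not on any one simulated figure.

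**What to change.** 1. In D.xi.1.a, state that the pairwise comparison of all infants as randomised, adjusted at most for pre-randomisation variables, decides the primary aim at 0.017.
2. In D.iii, remove the number of parasitaemia episodes from the model for the Cohort 1 versus Cohort 2 comparison, so that the two sections agree.
3. In D.xi.1.a, label the logistic model with first-year episodes, immune responses and parasite genotype as exploratory. Say that any cohort coefficient in it is not read as the effect of the intervention.

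The cost is a few sentences. No data are added, and the stated 78 per cohort (98 with losses) is unaffected because it already corresponds to a comparison without covariates.

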If the pregnant woman/mother is HIV-positive she will not be invited to participate in the study, and will be followed up at the Day Hospital following standard procedures, according to national guidelines, which includes HAART (see above for details). The investigators will not have access to any of the VCT center records and will receive no information at all on the HIV-status of women who are not enrolled in the study.

(Amended 15 October, 2004) (Amended 2 December, 2004) (Amended 11 July, 2005) (Amended 10 August, 2005)

iii. Experimental Cohorts

Infants who meet the criteria to participate in the study will be assigned to one of the 3 cohorts by block randomization, in order to adjust for seasonality of malaria infection. Thus, for every 6 infants, 2 will be randomized to each of the 3 cohorts. Enrollment of infants will continue over a one year period. Cohort 1 will receive chemoprophylaxis with SP+AS from 2 to 5 2,5 to 5,5 months of age (doses at months 2, 3 & 4 2,5; 3,5; 4,5) and placebo from 5 to 10 5,5 to 10,5 months of age. Cohort 2 will receive placebo from 2 to 5 2,5 to 5,5 months of age and chemoprophylaxis from 5-10 5,5 to 10,5 months of age (doses at months 5, 6, 7, 8 & 9 5,5; 6,5; 7,5; 8,5; 9,5), and Cohort 3 will receive placebo from 2 to 10 2,5 to 10,5 months of age. Placebo tablets will look exactly the same as the SP and AS tablets, with the same shape, size and colour. The treatment or placebo will be packed in individually numbered envelopes/bags. Doses of SP+AS/placebo will be administered on a monthly basis by a health assistant according to bodyweight (SP: single dose of 25 mg/kg Sulphadoxine and 1.25 mg/kg Pyrimethamine; AS: 4 mg/kg/day for three days). Tablets will be crushed and mixed with water on a tablespoon and administration will be directly observed. Infants will be observed for 30 minutes and a repeat dose will be given if vomiting occurs within that time. Infants from all three cohorts will be invited to the health post on month 2, 3, 4 and 9 to receive the EPI vaccines and the investigators will make sure they receive them. Subjects will be followed by active case detection as well as passive case detection until 10.5 months of age and by passive case detection and montly home visits from 10,5 to 25 24 months of age (see section v). (Amended 2 December, 2004) (Amended 11 July, 2005)

Rationale for the 3 cohorts:

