Treatment and follow-up: Any child with uncomplicated malaria will be treated as per standard of care in this area, currently with SP and Amodiaquine, the national first line antimalarial treatment. Children who have severe malaria will be transported by study vehicle to the Manhiça Hospital and referred to the intensive care unit for further care. As per standard of care at the Manhiça Hospital, they will have additional admission labs, including a CBC, glucose, blood culture, and lumbar puncture (if indicated) and will be treated with IV quinine and other support as needed, including intravenous hydration, anti-bacterials, or transfusion. After completing therapy, children will be followed up at routine weekly home visits. Those infants who fail therapy with SP plus Amodiaquine will be treated with a second-line treatment. For those children who have failed second line treatment, treatment will be given with oral quinine. One month after the infection first episode of malaria, the child will have another blood draw for immunological studies. (Amended 11 July, 2005)

v. Study Duration

A child's participation will continue until the child is 25 months of age unless the child is withdrawn, cannot tolerate SP+AS, or the family moves out of the study area. We anticipate a drop-out rate of 15% by the end of the second year and have adjusted our sample size accordingly.

Final protocol: 2nd July 2004 Amendment 1: 15th October 2004 Amendment 2: 2nd December 2004 Amendment 3: 11th July 2005 Amendment 4: 10th August 2005 Amendment 5: 12th September 2006 CONFIDENTIAL

Page 20 of 51

vi. Sample Collection

Field workers will be assigned to conduct the weekly active case detection. They will initially follow the pregnant women and then, upon enrollment of the infants, will be assigned a group of infants from each cohort. In addition, there will be staff available 24 hours a day, 7 days a week at the Ilha Josina *Maragra* Health Center *and Manhiça health center* to evaluate children who present with fever and/or symptoms of malaria. Microscopy and determination of Hematocrit can be performed at the Ilha Josina *Maragra* Health Center. Those samples requiring further work-up will be transported at 4 °C in coordinated transports from Ilha Josina *Maragra* to Manhiça. (Amended 15 October, 2004) (Amended 10 August, 2005)

The timepoints for collection of samples will be:

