(Amended 11 July, 2005) (Amended 10 August, 2005)

viii. Outcome Variables

1. Clinical outcome variables

a) Primary clinical outcome variable

The experience of having at least one episode of clinical malaria in the second year of life *detected by passive case detection.* (Amended 2 December, 2004)

b) Secondary clinical outcome variables

1. Fever (axillary temperature \geq 37.5° C or a history of fever in the previous 24 hours)

2. Hct during first, second and subsequent malaria infections, and during the **24 months** cross-sectional surveys.

3. Density of parasitemia during first, second and subsequent malaria infections, and during the **24** *months* cross-sectional surveys.

4. Time to first clinical episode during the second year of life *detected by passive case detection*.

5. Number of clinical episodes during the first year of life *detected by active or passive case detection*.

6. Number of clinical episodes during the second year of life *detected by passive case detection*. (Amended 2 December, 2004)

2. Immunological outcome variables

a) Primary immunological outcome variables:

 Anti-*Pt*EMP1 antibodies in peripheral blood, as measured at 0, 5, 10, 12, 15, 20 and 25 2.5, 5.5,
10.5, 15 and 24 months of age. The outcome variable to be compared between the cohorts will be: -Antibody units converted from median fluorescence intensity [31]

2. Level-Magnitude and frequency of cytokines (IFN- γ , IL-10) in peripheral blood in response to *in vitro* stimulation with Pf parasite antigens, as measured at 0, 5, 10, 12, 15, 20 and 25 2.5, 5.5, 10.5, 15 and 24 months of age

3. Ratio of Th1 (IFN- γ , TNF α , IL-12 and IL-2) to Th2 (IL-10, IL-5, IL-4) cytokines in plasma, as measured at 0, 5, 10, 12, 15, 20 and 25 **2.5, 5.5, 10.5, 15 and 24** months of age.

4. Anti-GPI antibodies in peripheral blood as measured at 2.5, 5.5, 10.5, 15 and 24 months of age. The outcome variables to be compared between the cohorts will be: -Antibody units converted from ELISA titre -Antibody units converted from Functional Neutralization Assay.

Final protocol: 2nd July 2004 Amendment 1: 15th October 2004 Amendment 2: 2nd December 2004 Amendment 3: 11th July 2005 Amendment 4: 10th August 2005 Amendment 5: 12th September 2006 CONFIDENTIAL

Page 24 of 51

CSI/CISM

5. Host genetics:

-Presence of homozygote or heterozygote for each particular SNP. -Presence or absence of nominated haplotype for each gene.

(Amended 11 July, 2005) (Amended 10 August, 2005)

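### Not tolerating SP+AS ends study participation rather than only dosing, so any drug-caused loss follows allocation and precedes the primary outcome window; the expected effect is small

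*Protocol*

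**What the plan says.** D.v (Study Duration) sets the rule: "participation will continue until the child is 25 months of age unless the child is withdrawn, cannot tolerate SP+AS, or the family moves" away. The three reasons stand in one list with the same consequence. No other section separates stopping study drug from leaving the study, and none says that a child who stops SP+AS keeps the home visits, the cross-sectional samples or passive case detection as a participant.

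D.iii (Experimental Cohorts) allocates equally: "for every 6 infants, 2 will be randomized to each of the 3 cohorts". Cohort 1 has active doses at 2.5, 3.5 and 4.5 months and then placebo. Cohort 2 has placebo and then active doses at 5.5, 6.5, 7.5, 8.5 and 9.5 months. For the third group, "Cohort 3 will receive placebo from 2 to 10 2,5 to 10,5 months of age" (replaced and replacing ages are both printed).

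The primary outcome in D.viii is "The experience of having at least one episode of clinical malaria in the second year of life", found by passive case detection; section C gives the window as 12-24 months. D.iv adds monthly home visits from 10.5 to 24 months and gives their purpose: "These visits will ensure that safety information on serious adverse events and deaths is captured".

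**The concern.** Stopping a drug and stopping observation are different events, and D.v joins them. True intolerance of SP+AS cannot arise in a cohort that never receives it, so drug-caused removals fall only on Cohorts 1 and 2. They happen after randomisation and before any of the outcome window: the last dose is at 9.5 months and counting starts at 12 months. The protocol gives no scientific reason to stop observing these children.

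Two things are at stake. The comparison of randomised cohorts would rest on children selected partly by their response to the drug. And a child with a suspected drug reaction would lose the home visits on which D.iv relies for serious adverse events. An analysis plan can choose an analysis population, but it cannot restore study data that were never collected.

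**Working it through.** **1. Reproduce the plan's own figures.** D.ix prints 78 evaluable children per cohort and 98 after 20% loss (replacing 65 and 77 at 15%).
- 78/(1 − 0.20) = 97.5, so 98; 65/(1 − 0.15) = 76.5, so 77. Both agree.
- D.ix gives a relative risk of 2 and an incidence of 0.4 per person-year without saying which cohort has 0.4. Taking risks of 0.20 and 0.40, two-sided 0.05 and 80% power, the unpooled formula gives (1.960 + 0.842)² × (0.20×0.80 + 0.40×0.60)/0.20² = 78.5, close to the printed 78. I use 0.20 and 0.40 below as an assumption that fits the plan.
- The final total is 350, so 350/3 = 116.7, about 117 per cohort.

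None of these figures covers intolerance. The drop-out allowance protects the number of children, not the balance between cohorts.

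**2. What the protocol says about intolerance (E.1.c, Potential Risks).**
- Allergic rash in about 1 in 20,000.
- An earlier infant trial of SP alone with no discontinuation because of the drug. E.1.c speaks of 701 infants given SP, but section B says that 701 were randomised to SP or placebo. Assuming that half had SP, 0 of about 350 has a one-sided 95% upper limit near 3/350 = 0.9%.
- No severe reaction attributed to treatment in 60 children given SP+AS. The upper limit is 1 − 0.05^(1/60) = 4.9%, for severe reactions only.

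D.v does not define intolerance, so no single figure applies. I take 1% and 5% as illustrative assumptions.

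**3. Children removed per active cohort of 117.**
- At 1 in 20,000: 117/20,000 = 0.006.
- At 1%: 1.2.
- At 5%: 5.9.

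**4. Bounds on the relative risk.** Let a fraction t of Cohort 2 be removed, with true risk 0.40 there and 0.20 in a comparator that loses no one. If all of the removed children would have had malaria, the observed risk is (0.40 − t)/(1 − t); if none would, it is 0.40/(1 − t).

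| t | Observed Cohort 2 risk | Observed relative risk (true 2.0) |
|---|---|---|
| 1% | 0.394 to 0.404 | 1.97 to 2.02 |
| 5% | 0.368 to 0.421 | 1.84 to 2.11 |

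This fits Cohort 2 against Cohort 3 when only drug-caused removal occurs. In Cohort 1 against Cohort 2 both can lose children. With equal loss t, (1 − t) cancels, and the widest range, reached only if the removed children were at opposite extremes in the two cohorts, is (0.40 − t)/0.20 to 0.40/(0.20 − t): 1.95 to 2.11 at 1%, and 1.75 to 2.67 at 5%.

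**5. Power.** With 20% other loss, 117 × 0.80 = 93.6 are evaluable. For two proportions with pooled null variance, power = Φ{[0.20√n − z√(2×0.30×0.70)]/√0.40}.
- At 0.05: 85.3%. Removing 1% from both compared cohorts gives 85.0%; 5% gives 83.5%.
- At the adjusted level of 0.017: 73.0%, then 72.5% and 70.4%.

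**The case against.** The strongest reply is that little primary outcome information need be lost. Passive case detection runs through facility morbidity surveillance, which D.i describes as a standard questionnaire for every child attending outpatients; E.1.b (Source Material) says that the trial's health-centre data come from that questionnaire. Deaths are followed through the demographic surveillance system (section C). This stands. A reader might infer from D.v that all outcome and safety data vanish for these children; the documents do not support that. What plainly ends is study home visits and study samples. Facility episodes would still be recorded, but the protocol does not say that the trial may use them once participation has ended.

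Second, the tablets look identical, so intolerance is judged blind and apparent intolerance of placebo could remove children from any cohort. This also stands. A reader might infer that Cohort 3 loses nobody under the rule; that does not follow. Only the drug-caused excess is tied to allocation.

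Third, the numbers are probably very small on the protocol's own safety figures. This largely stands. Those figures cover rash, SP given alone, or severe reactions in 60 children, so they do not exclude a few percent when intolerance is undefined.

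Fourth, reactions would be noticed before removal, because weekly visits during dosing ask about rash and other symptoms, and outpatient care stays open. True, but that does not replace study follow-up after the reaction.

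Finally, D.v is one sentence, apparently not updated: it still gives 25 months and 15% drop-out, where D.iii and D.iv use 24 months and D.ix also prints 20%. That argues for correcting the sentence. No other section overrides it.

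**Conclusion.** The point holds as a defect in a follow-up rule with a small expected effect. As written, D.v removes from study follow-up children who cannot tolerate SP+AS. The drug-caused part of that loss can arise only in Cohorts 1 and 2, precedes the whole primary outcome window, and is avoidable. It also conflicts with the stated safety purpose of the monthly visits.

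The effect is negligible at an assumed 1% removal from Cohort 2 and modest at 5%. These ranges rest on risks of 0.20 and 0.40, a comparator without loss, and removed children who all, or none, would have had malaria. The change in power is minor.

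A stronger conclusion, that the as-randomised comparison is broken, is not supported: the protocol nowhere says that these children are excluded from analysis, facility records may still exist for them, and its safety figures point to very few of them. The change is worth making because it is cheap and cannot be made afterwards.

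**What to change.** Reword D.v so that a child who stops study drug for any reason remains in study follow-up (home visits, passive case detection, and samples if the guardian agrees) to the end of the study and is analysed in the randomised cohort. Only withdrawal of consent, moving out of the area or death should end follow-up. Reconcile the age at end of follow-up and the drop-out figure in the same paragraph with D.iii, D.iv and D.ix.

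This does not alter who stops the drug or when; that clinical decision stays as it is. The cost is a short amendment and continued visits for a few children, using visits and case detection that are already in place.
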